2.4.5.2 Deaths

AEs leading to death will be listed.

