 - Concomitant medication
 - Study drug administration
 - PE information
 - Quality of life assessment: SF36 questionnaire
 - Adverse events
 - Physical examination, vital signs
 - Laboratory assessments:
 - Hematology (Hb, Hct, RBC, WBC, platelets)
 - Chemistry (AST, ALT, LDH, creatinine, protein, cholesterol and CRP)

- Organ damage marker: troponin (TnI)
- ADAMTS13 activity
- Immunogenicity: ADA panel
- Pharmacokinetics (not assessed if treatment with caplacizumab has not been initiated)
- PD parameters: vWF:Ag and RICO (the latter will not be assessed if treatment with caplacizumab has not been initiated).
- Urine:
 - Albumin
- Pregnancy test (blood or urine) for female subjects of childbearing potential (Note: pregnancy is an exclusion criterion for treatment with caplacizumab)

Statistics:**Main Endpoints**

- Proportion of subjects with TTP-related events (defined as TTP-related death, recurrence of TTP or reported major thromboembolic event), number of TTP-related events and time to event
- Mortality rate during the study
- Proportion of subjects with recurrence of disease, number of recurrences, and time to recurrence
- Proportion of subjects with reported major thromboembolic events (e.g., myocardial infarction, cerebrovascular accident, pulmonary embolism or deep venous thrombosis), number of events, and time to event
- Cognitive function
- Quality of life
- Immunogenicity of (repeated) treatment with caplacizumab

Statistical Methods

The sample size is not based on statistical considerations but rather on the number of subjects who complete Study ALX0681-C301 (HERCULES) and accept the option to participate in this FU Study (ALX0681-C302).

All subjects who enrolled in this FU study will be included in the safety and efficacy analyses. Statistical analyses are considered descriptive.

Interim analyses may be conducted in view of supporting regulatory submissions.

SCHEDULES OF ASSESSMENTS

Table 1: Schedule of assessments for twice yearly visits

Study Period	Screening/Baseline and Assessment Period (Months)						
	Screening/ Baseline ^a	6M FU visit (±1 month)	12M FU visit (±1 month)	18M FU visit (±1 month)	24M FU visit (±1 month)	30M FU visit (±1 month)	36M FU visit (±1 month)/ Early termination visit
Written informed consent	X						
Review of eligibility criteria	X						
Medical history ^b and demographics	X						
Concomitant medication							→
Adverse events							→
Supine heart rate & blood pressure ^c	X	X	X	X	X	X	X

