3.6.4. EVALUATION OF EFFICACY PARAMETERS

The following efficacy analyses will be performed:

- TTP-related events (defined as TTP-related death, recurrence of TTP or reported major thromboembolic event [e.g., myocardial infarction, cerebrovascular accident, pulmonary embolism or deep venous thrombosis]):
 - Summary of the (cumulative) proportion of subjects with TTP-related events over time (including after 12M FU visit, after 24M FU visit, and after 36M FU visit), as well as the number of such events.
 - Summary of the time to first TTP-related event (starting from screening/baseline visit), based on a Kaplan-Meier (KM) analysis.
- Mortality: mortality rate during the study.
- Recurrence of disease:
 - Summary of the (cumulative) proportion of subjects with recurrence of disease over time (including after 12M FU visit, after 24M FU visit, and after 36M FU visit), as well as the number of such events.
 - Summary of time to first recurrence (starting from end of previous TTP episode), based on a KM analysis.
 - Summary of TTP recurrence information, including duration of daily PE.
 - Descriptive analysis of incidence of recurrence in relation to ADAMTS13 levels after previous TTP episode.
- Reported major thromboembolic events (e.g., myocardial infarction, cerebrovascular accident, pulmonary embolism or deep venous thrombosis):
 - Summary of the (cumulative) proportion of subjects with reported major thromboembolic events over time (including after 12M FU visit, after 24M FU visit, and after 36M FU visit), as well as the number of such events.
 - Summary of the time to first reported major thromboembolic event (starting from screening/baseline visit), based on a KM analysis.
- Cognitive assessment:
 - Summary of RBANS cognitive assessment score, including change from baseline, over time.
 - Descriptive comparison of RBANS cognitive assessment score with reference population.
- Quality of life assessment:
 - Summary of HIT-6 scores, including change from baseline, over time.
 - Summary of SF-36 scales, including change from baseline, over time, and at the end of recurrence period.

All efficacy endpoints related to assessments on the Q6M FU visits will be analyzed using the ITO population. Summarization will be conducted on the total study population and by analysis group. For the group-wise analysis, the following groups will be considered:

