2.1.3.5.3 Death

Adverse event with a fatal outcome.

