2.1.4.2 Deaths

The deaths observation period is per the observation periods defined above.

- Death on-study: deaths occurring during the on-study observation period
- Death on-treatment: deaths occurring during the treatment-emergent adverse event period

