The following adverse event summaries will be generated by analysis period for the patients not treated in the recurrence population and for the ITO population.

- Overview of adverse events, summarizing number (%) of participants, the number of events, and the incidence per 100 person months, which will be calculated as: $100 \times (\text{Number of participants with AE}) / (\text{Total number of months observed within analysis period, summed for all participants})$ with any
 - Participants with at least one AE
 - Participants with at least one serious AE

- Participants with at least one AE leading to death
- Participants with at least one PE-related AE (only for the recurrence population)
- Participants with at least one serious PE-related AE (only for the recurrence population)
- Participants with at least one bleeding event, i.e. an event documented as event indicating an increased bleeding tendency
- Participants with at least one bleeding event, based on the Standardized MedDRA Query (SMQ) “Haemorrhage” with exclusion of the PT “TTP”
- Participants with at least one thromboembolic event, based on the SMQ “Embolic and thrombotic events” (arterial, venous, and vessel type unspecified and mixed arterial and venous) with exclusion of the PT “TTP”
- All AE by primary SOC and PT, showing the number (%) of participants with at least 1 AE. The number of events and the number and percentage of participants having an event will be presented.
- AEs will be summarized by SOC, PT and severity. This will be done for each analysis period. The number and percentage of participants having an event will be presented for the worst severity reported for each event.

Analysis of all treatment-emergent adverse events

The following treatment-emergent adverse event summaries will be generated by analysis period for the recurrence population.

- Overview of treatment-emergent adverse events, summarizing number (%) of participants, the number of events, and the incidence per 100 person months, which will be calculated as: $100 \times (\text{Number of participants with AE}) / (\text{Total number of months observed within analysis period, summed for all participants})$ with any
 - Participants with at least one TEAE
 - Participants with at least one serious TEAE
 - Participants with at least one TEAE leading to death
 - Participants with at least one TEAE for which the study drug was interrupted
 - Participants with at least one TEAE for which the study drug was withdrawn

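### The main endpoint mortality has no efficacy analysis of its own in the SAP; its crude rate appears only in adverse-event overview rows, split by ever-treated groups, with no total column and no interval

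*SAP*

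**What the plan says.** The protocol synopsis lists "Mortality rate during the study" second among its main endpoints. Protocol 3.6.4 repeats it among the efficacy analyses ("Mortality: mortality rate during the study") and adds nothing about landmark times, curves or intervals. For efficacy endpoints tied to the six-monthly visits, the same section says "Summarization will be conducted on the total study population and by analysis group". The groups are the C301 randomised arms, followed to the first recurrence, without subjects who had already recurred.

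The SAP deals with death in several places:

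- Section 2.1.3.5.3, among the efficacy endpoints, defines it as "Adverse event with a fatal outcome".
- Section 2.1.4.2 sets the windows, for example "Death on-study: deaths occurring during the on-study observation period".
- Section 2.4.4 (efficacy analyses) has no mortality item. TTP-related death enters only as a component of the TTP-related-event composite (2.1.3.5.1, 2.4.4.1).
- Section 2.4.5.2, headed Deaths, reads in full: "AEs leading to death will be listed".
- Section 2.4.5.1 plans for the ITO, over the whole study, an "Overview of adverse events, summarizing number (%) of participants, the number of events, and the incidence per 100 person months". One row is "Participants with at least one AE leading to death". A parallel row covers treatment-emergent events in recurrences.
- Section 2.4.5 splits the ITO safety tables into subjects who received caplacizumab at any time in C301, double-blind or open-label, and those who never did.
- Section 1.6 declares one change from the protocol, the dropped refractoriness endpoint.

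**The concern.** A reader who follows the main endpoint from protocol to SAP finds it defined under efficacy and then missing from the efficacy methods. The result has to be picked out of a safety table that the Deaths section does not point to.

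Three features of that table limit its use. First, the grouping. Protocol 1.2.4 says that C301 subjects with a first exacerbation, or a first relapse during treatment extension, cross over to open-label caplacizumab. A placebo subject with such an event is therefore counted with the caplacizumab subjects, and the never-treated group keeps the placebo subjects who did not cross over. A difference in mortality between the two groups would mix treatment with earlier disease course. Second, no column for the whole ITO is stated, although the study's third objective is to characterise the long-term impact of TTP. Third, no interval is given for a rate that will rest on very few deaths. Protocol 1.1 presents excess mortality after TTP as background, so readers will probably set the study's rate beside it.

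**Working it through.** **1. Does the overview row give a mortality rate?** The formula in SAP 2.4.5.1 is 100 × (participants with the event) / (total months observed). A subject dies once and observation ends at death, so for deaths recorded as fatal adverse events this is the crude mortality rate. For example, if 92 subjects (the approximate planned C301 size, Protocol 1.2.4) were each followed for 36 months and 3 died: 100 × 3 / (92 × 36) = 100 × 3 / 3312 = 0.091 per 100 person-months, or 1.09 per 100 person-years. The percentage beside it would be 3/92 = 3.3%.

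**2. What do the other event endpoints receive?**

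| Endpoint | Efficacy section in SAP | 12/24/36-month summary | Kaplan-Meier with 95% CI |
|---|---|---|---|
| TTP-related event | 2.4.4.1 | yes | yes |
| Major thromboembolic event | 2.4.4.2 | yes | yes |
| Recurrence | 2.4.4.3 | yes | yes |
| Mortality | none | no | no |

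Protocol 3.6.4 makes the same distinction for the landmark summaries and the curves: it asks for them for the first three and only for a rate for mortality.

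**3. How far could the grouping shift?** C301 planned about 92 subjects 1:1, so 46 per arm. Protocol 1.2.4 gives exacerbation in 28.2% of placebo subjects in the Phase II TTP study. If that held in C301, with every such subject crossing over and everyone enrolling here, 46 × 0.282 ≈ 13 placebo subjects would move. The ever-treated split would be 59 to 33, against 46 to 46 as randomised. With no crossover it stays 46 to 46. This is an illustration; the documents do not give the actual number.

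**4. How imprecise would the rate be?** Protocol 1.1 cites a registry report of 11 deaths in 57 patients over a median of 7.8 years. Treating the median as if it were the mean, 11 / (57 × 7.8) = 11 / 444.6 = 2.47 per 100 person-years. The study states no sample size, so assume 60 to 92 enrolled, 3 years each, and a constant rate:

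- 60 × 3 = 180 person-years; expected deaths 0.0247 × 180 = 4.5
- 92 × 3 = 276 person-years; expected deaths 0.0247 × 276 = 6.8

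The exact Poisson 95% limits for d deaths in T person-years are χ²(0.025; 2d)/(2T) and χ²(0.975; 2d+2)/(2T):

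| Deaths / person-years | Rate per 100 person-years | 95% CI | Upper / lower |
|---|---|---|---|
| 4 / 180 | 2.2 | 0.61 to 5.69 | 9.3 |
| 7 / 276 | 2.5 | 1.02 to 5.23 | 5.1 |

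Fewer deaths would be less precise still. In the step 1 example, 3 deaths in 3312 person-months give 0.091 per 100 person-months with limits 0.019 to 0.265, a 14-fold range.

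**The case against.** The strongest reply is that the SAP does what the protocol asks. The protocol wants a mortality rate during the study, and the overview row supplies one on the ITO for the overall study period. This stands. A reader who sees only Section 2.4.5.2 might infer that deaths are merely listed, or that mortality has no analysis and no time scale; Section 2.4.5.1 contradicts all three.

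A reader might also take the missing curve, landmark estimates and interval as departures that Section 1.6 should have declared. They are not: the protocol requests none of them for mortality, and the study is descriptive.

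Nor does the planned output simply treat patients who left as alive. That is a fair criticism of the percentage, but the person-month rate stops counting subjects when observation stops.

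On grouping, the protocol's group-wise rule is worded for endpoints assessed at the six-monthly visits, so its application to mortality is likely but not explicit. Taken literally, it would also drop deaths after a first recurrence, which is not mortality during the study. With open-label crossover in C301, an ever-treated split is defensible for safety tables. The two safety groups together make up the ITO, so a reader could add them to get a total and compute an interval by hand. All this is true, but it leaves the reader to assemble a main endpoint from a safety table, and the only between-group display is one that recurrence partly determines.

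**Conclusion.** The concern holds as a gap in how a main endpoint is presented and grouped. The SAP delivers a crude mortality rate, but outside the efficacy section and without a cross-reference. The split is affected by crossover after recurrence, and no total column or confidence interval is stated. The other three event endpoints have intervals and curves.

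The case for an interval rests on small numbers. With 4 to 7 deaths the upper 95% limit is about 5 to 9 times the lower. That range depends on an assumed 60 to 92 enrolled (only the 92 comes from the documents, as the approximate planned size of C301), 3 full years each, and a constant rate taken from a registry median. The grouping and presentation points do not depend on these assumptions. This is a cheap improvement that should be made; it does not show that the protocol was breached or that mortality goes unreported.

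**What to change.** Add a short mortality subsection to SAP 2.4.4 and refer to it from 2.4.5.2. On the ITO, report all-cause deaths, person-years, the rate per 100 person-years with an exact Poisson 95% interval, and Kaplan-Meier mortality at 12, 24 and 36 months with 95% intervals, censoring at the date last known alive. Show this for the total ITO and by C301 randomised arm over full follow-up. Keep the comparison descriptive, since only subjects who completed C301 and opted in are included. If the Section 2.4.4 analysis groups are shown as well, state that their follow-up stops at first recurrence and that subjects with earlier recurrences are left out.

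Keep the overview row and the listing. State one limit: Protocol 3.2.4.1 allows no further assessments after loss to follow-up or withdrawal of consent, so later deaths in those subjects cannot be captured.

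The cost is some SAP text, one table and one figure from data already collected. The intervals will be wide, and with so few deaths the curve will add little beyond the landmark estimates.

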2.4.5.3 Analyses of laboratory variables

Laboratory analyses will be performed on the ITO and recurrence populations using the corresponding baseline visits.

All values will be compared to their matching normal ranges. The classification available in the standard data tabulation method (SDTM) dataset will not be used for the statistical analysis. The classification will be re-calculated in the analysis data model (ADaM) dataset by using the values and normal ranges in standard international (SI) units.

Values will be scored as abnormal low (L), normal (N) or abnormal high (H). A value is classified as abnormal low when the value < lower limit of the normal (LLN) range. A value is classified as abnormal high when the value > upper limit of the normal (ULN) range. Tests without normal ranges will not be scored. An original value like "<X" where X equals the lower limit of the normal range will be classified as abnormal low (L). An original value like ">X" where X equals the upper limit of the normal range will be classified as abnormal high (H).

The worst-case abnormality is derived for each parameter separately. All non-missing post-baseline values (including unscheduled measurements and follow-up measurements) will be used to derive the following worst-case:

- H = abnormal high: at least one post-dose measurement is above the normal range, and there are no values below the normal range.
- L = abnormal low: at least one post-dose measurement is below the normal range, and there are no values above the normal range.
- H+L = abnormal high and low: at least one post-dose measurement is above the normal range, and at least one other post-dose measurement is below the normal range.

N = normal: all post-dose measurements are within normal limits.

The summary statistics (including number, mean, median, Q1, Q3, standard deviation, minimum and maximum) of all laboratory variables (actual values and changes from baseline) will be calculated for each visit or study assessment (baseline, each postbaseline time point) by treatment group.

A shift table will be created per laboratory parameter. The table will present the shift in abnormality (L/N/H) at each post-baseline time point versus the baseline abnormality (L/N/H). Laboratory parameters without normal ranges will not be presented in this table. In addition, the tables that present the shift in abnormality (L/N/H/L+H) at the worst post-baseline time point versus the baseline abnormality (L/N/H) will also be created.

Laboratory variables will be listed. All data scored as out-of-normal-range or clinically significant will also be listed.

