[figure not shown]
collected as will safety information (including AEs, safety laboratory parameters, vital signs and physical examination), and determination of PK, ADA, PD parameters (vWF:Ag and RICO), and disease-related markers (ADAMTS13 activity and TnI).

In case of recurrent thrombocytopenia requiring re-initiation of daily PE during an ongoing recurrence period (see [Figure 4](#) and [Table 2](#)), a new visit cycle is to be started, with a recurrence visit on the day of the new recurrence followed by all subsequent visits as indicated in [Table 2](#). All remaining visits of the original schedule are no longer applicable and are not to be performed.

Note: an i.v. loading dose of caplacizumab needs to be administered prior to re-initiation of PE for the recurrence.

Q6M visits that are scheduled within a recurrence period will not be held as assessments at such visits would be confounded by the concurrent recurrence.

Note: Treatment with caplacizumab may not be initiated for subjects who do not fulfil the caplacizumab treatment criteria (see section [3.2.3](#)). Hence, these subjects will be treated with standard of care only. The visit schedule in case of initiation of only standard of care treatment includes a recurrence visit at presentation and a recurrence FU visit at 30 days after end of daily PE (see [Appendix 1](#) for schedule of assessments).

M: month; Y: year

Figure 4: Study flow of Study ALX0681-C302.

Treatment in case of recurrence:

Standard of care treatment (per standard site practice) can include:

- PE with plasma (e.g., fresh frozen plasma, solvent detergent/viral-inactivated plasma, cryosupernatant)
- Corticosteroid treatment
- Use of other immunosuppressive agents (e.g., rituximab)

Initiation of treatment with caplacizumab^{§§}:

Daily PE period

- Loading i.v. dose: subjects will receive a single loading dose of 10 mg study drug by i.v. bolus injection from 6 hours to 15 minutes prior to start of daily PE treatment^{***}.
- Daily s.c. dose: within 2 hours after completing each daily PE, a s.c. injection of 10 mg study drug will be administered daily throughout the full duration of PE treatment.

30-day post-daily PE period

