3.6.6. EVALUATION OF SAFETY PARAMETERS

The DSMB will evaluate the safety data periodically (see section [3.1](#)).

The following analyses will be performed to assess the safety of subjects in this study.

- The incidence and type of AEs.
- The incidence and type of SAEs.
- The incidence and type of related AEs (including bleeding-related AEs, PE-related AEs, and corticosteroid-related AEs).
- The laboratory parameters and change from baseline in these laboratory parameters.

All safety analyses will be performed using the ITO population for the overall study period and using the recurrence population for recurrence periods specifically. Details will be provided in the SAP.

AEs will be fully described and coded according to the Medical Dictionary for regulatory Activities (MedDRA). Frequency of subjects presenting AEs, AEs leading to discontinuation of study drug, adverse drug reactions, and SAEs will be tabulated by system organ class and preferred term. AEs of special interest will be analyzed separately.

For laboratory parameters, descriptive statistics (mean, median, standard deviation, minimum, and maximum) will be computed on the actual values and the change from baseline. All laboratory values will be categorized according to their normal ranges as below, within or above normal. A shift table versus baseline will be created.

Vital signs variables will be fully depicted using descriptive statistics.

Abnormal findings in physical examinations will be listed.

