1.3 DETERMINATION OF SAMPLE SIZE

The sample size is not based on statistical considerations but rather on the number of subjects who complete Study ALX0681-C301 (HERCULES) and accept the option to participate in this FU study (ALX0681-C302). All subjects who enrolled in this FU study will be included in the safety and efficacy analyses.

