2.1.3.5.4 Recurrence of aTTP

A recurrence of aTTP is defined as recurrent thrombocytopenia requiring initiation of daily plasma exchange (PE).

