2.5.5 Unscheduled visits

For the assessment of the Q6M FU visits, the closest visit to the planned Q6M FU visit date will be used for summary statistics.

Unscheduled measurements will be taken into account for derivation of time to event parameters. They will also be used if there is a worst-case determination or abnormality over a period of time.

All values will be listed.

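### As most naturally read, the ITO worst-case laboratory shift table includes values drawn during TTP recurrences, so its platelet shifts (and plausibly LDH and haemoglobin) cannot be separated from relapse

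*SAP*

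**What the plan says.** - **Populations and baselines (SAP 2.4.5.3).** "Laboratory analyses will be performed on the ITO and recurrence populations using the corresponding baseline visits".
- **Values used (SAP 2.4.5.3).** "All non-missing post-baseline values (including unscheduled measurements and follow-up measurements) will be used to derive the following worst-case". The result (H, L, H+L or N) feeds a shift table of worst category against baseline category, in addition to a shift table by time point. The category definitions speak of *post-dose* measurements, although the rule and the table description say *post-baseline*.
- **Period (protocol 3.6.6).** "All safety analyses will be performed using the ITO population for the overall study period and using the recurrence population for recurrence periods specifically". SAP 2.1.4 lets the on-study and recurrence periods overlap, and SAP Table 3 runs the Observation phase from screening/baseline to the end of participation.
- **Unscheduled values (SAP 2.5.5).** "They will also be used if there is a worst-case determination or abnormality over a period of time". Local platelet and LDH results obtained during a recurrence are also collected where available (SAP Table 5, footnote e).
- **Groups (SAP 2.4.5).** *Caplacizumab total* received the drug in C301, double-blind or open-label; *Not treated* never received it in C301. Neither group is cut at a recurrence in C302.
- **How recurrences are treated elsewhere.** SAP 2.4.4 follows the efficacy groups only to first recurrence and drops subjects who recurred in C301 or before the C302 baseline. Protocol 3.1.1 says that Q6M visits falling in a recurrence period "will not be held as assessments at such visits would be confounded by the concurrent recurrence".

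**The concern.** An ITO worst-case table is normally read as a summary of long-term laboratory safety. Here a single extreme value fixes a subject's category, and the most extreme platelet values will usually come from an acute recurrence, which SAP 2.1.3.5.4 defines by thrombocytopenia. LDH and haemoglobin are plausibly affected too, because the disease is haemolytic. The protocol cancels Q6M visits during a recurrence because their data would be confounded. The worst-case rule then lets values from the same days into the ITO summary.

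The group comparison is the more serious matter. A *Not treated* subject who relapses in C302 receives open-label caplacizumab unless the treatment criteria bar it, so on-drug values appear under that label. *Caplacizumab total* can include placebo subjects who recurred in C301 and crossed over to open-label drug (protocol 1.2.4). The two groups may therefore differ in relapse history, and the table could present that as a laboratory difference due to the drug.

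**Working it through.** **1. Draws per recurrence, checked against the plan's own figure.** Protocol 3.4.10 gives about 182 mL without a recurrence and 560 mL with one.
- Q6M schedule: baseline plus 6 visits = 7 visits; 182 / 7 = 26 mL per visit.
- A recurrence visit adds 2.0 mL for PK (3.4.5.1) and 3.5 mL for RICO (3.4.6.1): 26 + 2.0 + 3.5 = 31.5 mL.
- (560 − 182) / 31.5 = 12 visits. The stated 560 mL is reproduced exactly.
- Protocol Table 2 gives the same count: recurrence visit, Day 3, post-PE Days 1, 8, 15, 22 and 29, four extension weeks, and the FU visit. Without extension there are 8 visits (182 + 8 × 31.5 = 434 mL). A recurrence not treated with caplacizumab has 2 (Appendix 1).

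Scheduled post-baseline draws are therefore 6 with no recurrence, 8 with one untreated recurrence, and 14 to 18 with one treated recurrence, less any Q6M visit cancelled during it.

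**2. Effect of sampling frequency alone.** Assume that each value has a 5% chance of lying outside a 95% reference range, independently. The chance of at least one abnormal value is 1 − 0.95^n: 26.5% for n = 6, 33.7% for n = 8, 51.2% for n = 14 and 60.3% for n = 18. This is before any disease or drug effect.

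**3. Any low platelet value (L or H+L).** Let r be the share of subjects who relapse, with a low value recorded in every relapser, and q the chance of a low value in Q6M data. The share with any low value is r + (1 − r)q; relapsers make up r / [r + (1 − r)q] of it. If recurrence values are left out, the share is q.

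Protocol 1.1 gives r = 18% (range 3% to 84%). The documents give no q. With an assumed 2.5% per visit, q = 1 − 0.975^6 = 14.1%; the assumed range is 5% to 30%. Each cell shows the share with any low value, then the relapsers' part of it.

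| r | q = 5% | q = 14.1% | q = 30% |
|---|---|---|---|
| 3% | 7.9%; 38% | 16.7%; 18% | 32.1%; 9% |
| 18% | 22.1%; 81% | 29.6%; 61% | 42.6%; 42% |
| 84% | 84.8%; 99% | 86.3%; 97% | 88.8%; 95% |

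**4. Group difference.** If two groups share the same q but relapse at rates rA and rB, the table shows a difference of (rA − rB)(1 − q). An illustrative 10-point gap in relapse gives 9.5, 8.6 or 7.0 points at q = 5%, 14.1% or 30%. With recurrence values left out it is 0.

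**The case against.** The strongest objection is that recurrence values may never have been meant for this table. SAP 2.3.1 assigns the ITO population to Q6M data, SAP 2.3.2 assigns recurrence-period data to the recurrence population, and SAP 2.4.5 pairs the screening/baseline value with the Q6M visits. That reading is open, so inclusion is an inference and not an explicit statement. It is still the more natural inference: 2.3.1 applies only where nothing else is specified, and the worst-case rule does specify, naming unscheduled and follow-up values. Two programmers could build two different tables.

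An all-inclusive worst case is also a defensible safety summary, and protocol 3.6.6 asks for the overall study period. That stands, and it is a reason to keep such a table. It does not justify using it alone for the comparison by C301 exposure. Everything here is descriptive, and by-visit shift tables, by-visit summaries and listings remain. They soften the problem, though SAP 2.5.5 does not say whether a recurrence visit may stand in as the closest visit to a cancelled Q6M visit.

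A reader might go further on three points, which the documents do not support:
- *Every relapser is scored L.* Under SAP 2.4.5.3 a subject with both a low and a high value is H+L, and one already low at baseline is not an N-to-L shift.
- *The Phase II rates of 33.3% and 36.1% apply.* They combine exacerbations and relapses after an acute episode (protocol 1.2.4). C302 enrols subjects who have completed the final 28-day follow-up visit of C301 and are past that early window.
- *The table shows only who relapsed and says nothing about long-term safety.* Subjects without a recurrence are unaffected, the argument is weak for parameters such as WBC, protein and cholesterol, and at 3% recurrence most subjects with a low platelet value did not relapse in two of the three assumed backgrounds and in the third still outnumber relapsers.

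**Conclusion.** The point holds in a limited form. As most naturally read, the ITO worst case includes recurrence values, and no passage excludes them. For platelets, and plausibly LDH and haemoglobin, worst-case shifts and differences by C301 exposure cannot be separated from relapse, denser sampling and open-label caplacizumab in C302.

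The size depends on the recurrence rate. With q = 14.1%, recurrence values roughly double the share with any low platelet value at r = 18% (14.1% to 29.6%), add little at r = 3% (to 16.7%) and dominate at r = 84% (to 86.3%). These figures assume independent values, the stated background rates and a recorded low value in every relapser. The count of 8 to 12 added draws is for a treated recurrence, with 12 the full-extension maximum. The *post-dose* wording is a separate, small defect: ITO subjects without a recurrence receive no dose in C302, so those definitions do not literally fit them.

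**What to change.** In SAP 2.4.5.3:
1. Derive the ITO worst case by group from values outside recurrence periods, using the episode start and end dates in SAP Tables 1 and 2.
2. Report the recurrence-period worst case in the recurrence population, against the recurrence-visit baseline.
3. Keep the worst case over the overall study period as a supplementary ITO table, so that protocol 3.6.6 is still met.
4. Replace *post-dose* by *post-baseline* in the category definitions for ITO.
5. State whether local platelet and LDH results enter the derivation.

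The cost is one extra table and a period filter on dates already defined. No new data are needed, and the by-visit shift tables and listings do not change.
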